**PROTOCOL TITLE: Efficacy of superior laryngeal nerve block for chronic cough****PRINCIPAL INVESTIGATOR: [name]****1.0 Objectives / Specific Aims**

**AIM:** Determine the overall efficacy of superior laryngeal nerve blocks for the treatment of neurogenic chronic cough. This is the primary aim of the study: to test the hypothesis that superior laryngeal nerve blocks are an effective treatment for neurogenic cough based on existing retrospective data. This will be achieved through the design of a prospective, single-blind, randomized clinical trial in which one group of patients will undergo a series of two standard (steroid-lidocaine mixture) injections and the second group will undergo a series of two placebo (saline) injections. By determining if a clinically significant difference exists between the outcomes of the two groups, measured by a dichotomous yes/no response to improvement, the Leicester Cough Questionnaire, and a visual analogue scale for symptom severity. This will provide the answer to the general question of whether or not these injections are clinically effective for patients with neurogenic cough. Furthermore, any adverse reactions will be thoroughly documented. The significance of this specific aim is to confirm the clinical utility of superior laryngeal nerve blocks; if proven effective, this can greatly improve the care of these patients by allowing for an evidence-based treatment option.

Given the focus and timeframe of the proposed project, this one aim to determine overall efficacy is sufficient; however, it could be further subdivided:

**Aim 1a:** Determine if patients who undergo a series of superior laryngeal nerve blocks report improvement in cough severity and quality of life.

**Aim 1b:** Determine the placebo effect of superior laryngeal nerve blocks in the treatment of neurogenic chronic cough.

**Aim 1c:** Determine the average amount of time post-injection at which symptoms return.

**Aim 1d:** Determine the rate of complications of in-office superior laryngeal nerve blocks.

By confirming the efficacy found in retrospective studies and developing an optimal protocol for these injections, this project overall aims to improve evidence-based treatment options for patients with neurogenic cough. This has the potential to shift the treatment paradigm for this disease process from daily dosing of a neuromodulating medication to local therapy directed at the superior laryngeal nerve. For patients diagnosed with neurogenic cough, the findings of this study could have a significant impact on limiting or eliminating their symptoms and improving quality of life.

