## **6.0 Number of Subjects**

We will recruit 50 patients. Our institution has several otolaryngologists who routinely treat chronic cough and, within the past year, a single provider performed superior laryngeal nerve blocks on 29 patients, with the majority of the injections occurring within the last 2-3 months. Therefore, we are confident in our ability to recruit 50 patients within 1 year. Assuming a dichotomous outcome of >50% improvement or not, a 70% treatment effect, a 25% possible incidence of improvement in placebo, and an 80% confidence level, we would need 18 patients in each group (total N=36) to power our study.

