## **10.0 Study Design / Methods**

Figure 2 depicts the flow diagram of the study design. Once patients have met inclusion and exclusion criteria (including undergoing all diagnostic testing for other potential causes of chronic cough) and have agreed to study participation, informed consent will be obtained and they will be randomized into two groups: treatment and placebo. This will be achieved using randomly-assorted, secured envelopes containing a card indicating whether the patient will be in the treatment or placebo group. This will be unveiled immediately to the provider administering the first injection, but remain unknown to the subject. There will be 25 "Treatment" and 25 "Placebo" cards within the 50, individually-secured envelopes. On initial visit, prior to the injection, patients will first undergo nasal laryngoscopy as part of standard of care. If there is any vocal fold weakness seen on scope examination or if there is a unilateral trigger point identified, then the first injection will start on the side of the suspected neuropathy. If there is no evidence of neuropathy on examination, we will start with a left-sided injection. Injections will be standardized to 2 mL of a 1:1 triamcinolone 40mg: 1% lidocaine with 1:200,000 epinephrine. Injection syringe will be brought into room by the physician in an opaque box and placed behind patient so they cannot view the syringe prior to injection. During the injection, a paper "shield" will be held under the patient's chin by an assistant and they will be asked to close their eyes so that they are not able to view the syringe during injection. This is necessary as steroid possesses a white color as compared to clear saline. The practitioner is not blinded so that proper drawing back on the syringe is not compromised to avoid intravascular or airway injection.

[figure not shown]

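### Optional Aim 1b asks for the placebo effect, but two arms (active and saline) can give only the total response in the saline arm

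*Combined protocol and SAP*

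**What the plan says.** Section 1.0 sets one efficacy aim, resting on the difference in outcomes between the two groups. It then says that "this one aim to determine overall efficacy is sufficient; however, it could be further subdivided", and lists four sub-aims. Aim 1b is "Determine the placebo effect of superior laryngeal nerve blocks in the treatment of neurogenic chronic cough".

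On design, Section 10.0 says of eligible, consented patients that "they will be randomized into two groups: treatment and placebo", with 25 allocation cards for each. No third group is described. The daily visual analogue diary is kept after each injection, and no period of recording before treatment is described. Two weeks after the second injection patients are unblinded, and those who had saline may take two open-label active injections.

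On analysis, Section 12.0 gives percentages per group per injection with a chi-squared test, a regression and t-test for the Leicester Cough Questionnaire (LCQ), a regression on the diary scores, and a comparison of the placebo group's pre-unblinding data with its later active injections. No analysis is labelled as answering Aim 1b.

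The only figure for the saline arm is in Section 6.0, which assumes "a 25% possible incidence of improvement in placebo" for a dichotomous outcome of more than 50% improvement.

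**The concern.** A placebo effect is the difference between receiving a sham treatment and receiving none. Estimating it needs some record of what happens without treatment, from an untreated group or at least from a run-in. This design has neither, so patients in the saline arm who improve may have done so through a response to the injection procedure, through the ordinary course of the condition, or because they enrolled when the cough was worse than usual for them.

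The label matters because Section 2.0 names the potential for placebo effect as a particular open question about these injections. A reader of the results will look for that number, and Aim 1b invites the saline arm's improvement to be given as the answer. That conclusion would go beyond what the design can support.

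**Working it through.** **The plan's own figure.** Section 6.0 assumes "a 70% treatment effect, a 25% possible incidence of improvement in placebo, and an 80% confidence level" and arrives at 18 per group. I read the 70% as the active response rate and the 80% as power, and assume two-sided alpha of 0.05, which is not stated.
- Arcsine formula: h = 2·asin(√0.70) − 2·asin(√0.25) = 0.935; n = 2(1.960 + 0.842)²/h² = 17.95, so 18 per group.
- Pooled normal formula: n = [1.960·√(2 × 0.475 × 0.525) + 0.842·√(0.21 + 0.1875)]²/0.45² = 18.1, so 19 per group.

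The stated size reproduces and is not in dispute. It concerns the active-versus-saline contrast only.

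**What the two arms identify.** Write D for the drug effect, P for the placebo effect, and N for natural course plus regression to the mean, taken as additive.
- Saline arm: P + N
- Active arm: D + P + N
- Active minus saline: D

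There are two equations and three unknowns. They give D and the sum P + N, but never P alone. More patients estimate P + N more precisely and do not split it.

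**Does the comparison after unblinding help?** Mark the values in the later open-label period with a prime. Later active minus earlier saline is D + (P′ − P) + (N′ − N). The comparison is sequential and unblinded, and it is restricted to patients who take up the offer. It sets active against saline, with no untreated period in either term, so P is still not isolated.

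**Size on the protocol's assumption.** If the saline response is 25% and p0 of that would have occurred untreated, the placebo share is 25% − p0. The documents give no p0, so the values below are assumptions. The last two columns show what a saline-versus-untreated comparison would require (two-sided 0.05, 80% power, pooled formula).

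| Assumed p0 | Placebo share (points) | Needed per arm | Power with 25 per arm |
|---|---|---|---|
| about 0% | 25 | 27 | 78% |
| 5% | 20 | 49 | 51% |
| 10% | 15 | 100 | 28% |
| 15% | 10 | 250 | 14% |
| 20% | 5 | 1,094 | 6% |

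**Regression to the mean on a continuous score (illustration, assumed values).** If baseline is m SD worse than the patients' usual level and the test-retest correlation is r, the expected apparent improvement is (1 − r)·m. With m = 1, this is 0.4 SD at r = 0.6 and 0.1 SD at r = 0.9.

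**Precision, a separate matter.** Six of 25 (24%) has a Wilson 95% interval with centre 0.275 and half-width 0.160, giving 11.5% to 43.4%. The exact interval is 9% to 45%. This describes how well the total saline response would be known and says nothing about how it divides.

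**The case against.** The strongest reply is that this is terminology. The sub-aims are an optional subdivision of a single aim that the protocol calls sufficient, and Aim 1b has no endpoint, sample-size basis or analysis of its own. The protocol also uses the term loosely, and Section 6.0 speaks simply of improvement in placebo. If placebo effect means response in the placebo arm, the percentages per group in Section 12.0 already supply it. This stands as to weight and explains why the point is minor. It does not make the wording right, since under that reading the aim should simply say so.

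It can also be said that the documents do not show natural course or regression to the mean to be important here. Section 2.0 calls the nerve hypersensitivity likely post-viral but does not mention spontaneous recovery, Table 1 sets no minimum severity, and nothing says that patients enrol at a symptom peak. That is fair, and it means their size is unknown. It does not allow them to be taken as zero.

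A reader might go further and infer that Aim 1a, "Determine if patients who undergo a series of superior laryngeal nerve blocks report improvement in cough severity and quality of life", has the same fault. The documents do not support this. Section 1.0 rests efficacy on the difference between the two groups, Section 12.0 compares the arms by chi-squared and t-test, and nothing says that Aim 1a will be answered from the treated arm alone.

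A reader might also infer that the trial will publish an overstated placebo effect. No section says that the saline arm's change will be reported under that name, and overstatement by any particular amount cannot be shown. The wording creates a risk and does not amount to a plan.

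**Conclusion.** The point holds for Aim 1b and is minor. As worded, the aim asks for a quantity that active and saline arms without an untreated reference or run-in cannot isolate, and the comparison after unblinding does not supply what is missing. On the protocol's 25% the placebo share is unidentified between 0 and 25 points. That range assumes additive, non-negative components and uses a planning figure for more than 50% improvement, so it shows the scale of the ambiguity and does not estimate it.

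It would be wrong to infer that the trial's main conclusion is weakened. Natural course and regression to the mean are expected to be equal in the two randomised arms, so this point leaves the active-versus-saline comparison, the sample size and the data collection as they are. Nor does it call for a third arm: with 25 per arm, such a comparison would have at most about 78% power, even if almost no untreated patient improved.

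**What to change.** Restate Aim 1b along these lines: *estimate the response in the saline arm (placebo effect, natural course and regression to the mean combined), with a 95% confidence interval*. Add to Section 12.0 that this figure will not be reported as a placebo effect. Aim 1a needs no change on this account.

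The cost is a narrower claim than the one now stated. No arm, visit, patient or measurement is added; the only extra analysis is a confidence interval around a percentage that Section 12.0 already plans to tabulate.

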### **Figure 2. Flow Diagram of Study Design**

Injection will be completed near the lateral thyrohyoid membrane by a single experienced laryngologist per previously published methodology utilizing bony, soft tissue and cartilaginous landmarks. An illustration of the anatomic target for the injection can be seen in Figure 3. To minimize patient discomfort, lidocaine cream will be applied to the skin prior to injections.

Following injection, patients will be instructed to follow up in a 2- to 3-week time frame; however, we will include all patients in analysis if they follow up within 1-4 weeks. Any follow up outside of that window will lead to removal of the patient's data from the analysis. At follow up, if the patient's cough has improved by greater than or equal to 50% compared to baseline, we will repeat the injection on the same side. If less than 50%, we will move to the other side to perform the injection. Patients will undergo a total of two injections before data collection is complete for analysis. If patients were to experience full resolution of cough (i.e. report 0/10 for cough severity) after the first injection alone, then at that point, their condition would be considered cured and their enrollment in the study will finish. The reason for this is to avoid unnecessary and unindicated injections in patients with resolution of cough.

2 weeks after the second injection, participants will be unblinded. If in the placebo group, they will have the opportunity to complete 2 additional treatment injections (unblinded) under the study protocol. Data will be collected and stored in the same fashion as prior to unblinding.

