**Figure 3. Anatomic Target of Superior Laryngeal Nerve Blocks.**

During the procedure, the thyroid cartilage, hyoid, and thyrohyoid membrane are palpated as key anatomic landmarks. The target of the injection, the superior laryngeal nerve, pierces the thyrohyoid membrane superior to the superior laryngeal artery. The plunger is drawn back prior to injection to ensure needle tip is not intravascular. Illustration by author.

Patients will be provided a log to track their progress throughout treatment. This will include a visual analogue scale to be completed daily after each injection to document cough severity, as well as opportunities to document any adverse effects or general comments. An example of this log can be seen in Figure 4. At each follow up visit, patients will provide a dichotomous answer (Yes or No) if they experienced improvement in cough and will disclose how long the improvement lasted. They will also fill out the Leicester Cough Questionnaire (LCQ), a validated 19-question quality of life survey for chronic cough. The LCQ will be the study's primary outcome measure. Please see Appendix 1 for a copy of the Leicester Cough Questionnaire. After the last injection, patients will return to the clinic in three months or opt to be contacted via telephone to assess if symptoms have returned.

Date of last injection: _____
 
WEEK 1  Please mark on the line below with a "X" how severe you believe your cough is. The far left indicates no cough at all, and the far right is indicative of the most severe cough.
 
Day 1 no cough ..... severe cough
 
Day 2 no cough ..... severe cough
 
Day 3 no cough ..... severe cough
 
Day 4 no cough ..... severe cough
 
Day 5 no cough ..... severe cough
 
Day 6 no cough ..... severe cough
 
Day 7 no cough ..... severe cough
	

Date of last injection: _____
 
WEEK 2  Please mark on the line below with a "X" how severe you believe your cough is. The far left indicates no cough at all, and the far right is indicative of the most severe cough.
 
Day 1 no cough ..... severe cough
 
Day 2 no cough ..... severe cough
 
Day 3 no cough ..... severe cough
 
Day 4 no cough ..... severe cough
 
Day 5 no cough ..... severe cough
 
Day 6 no cough ..... severe cough
 
Day 7 no cough ..... severe cough
	

Any side effects?
	
Any side effects?

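### Aim 1c asks for an average time to symptom return, but many return times will be incomplete and the plan has no method for them

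*Combined protocol and SAP*

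**What the plan says.** All references are to the combined protocol and SAP.

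- **Section 1.0, Aim 1c:** "Determine the average amount of time post-injection at which symptoms return". It does not say which injection or arm is meant, or what counts as return.
- **Section 10.0, timing of injection 2:** "Following injection, patients will be instructed to follow up in a 2- to 3-week time frame", and "we will include all patients in analysis if they follow up within 1-4 weeks". Injection 2 also goes to responders: those at least 50% better than baseline are re-injected on the same side.
- **Section 10.0, early exit:** for patients reporting 0/10 after injection 1, "their condition would be considered cured and their enrollment in the study will finish".
- **Section 10.0, crossover:** participants are unblinded two weeks after injection 2. For those who had placebo, "they will have the opportunity to complete 2 additional treatment injections (unblinded) under the study protocol".
- **Section 10.0, how duration is learned:** patients keep a daily visual analogue log and state at each follow-up visit how long any improvement lasted. The closing step, timed from the final injection, is a single contact: "patients will return to the clinic in three months or opt to be contacted via telephone to assess if symptoms have returned".
- **Section 12.0, analysis:** chi-squared tests, linear regression and a t-test on LCQ changes, and regression on the daily log. No analysis is tied to Aim 1c, and nothing is said about patients whose cough has not returned.

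**The concern.** Time to return is a time-to-event quantity, and an ordinary average needs every patient's time. Here many will be missing, and those missing are mainly the long ones:

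- A responder to injection 1 is re-injected within weeks, so the duration of that first response is not seen.
- A patient at 0/10 leaves with no return time, although this may be one of the longest responses.
- A patient still improved at three months has no return time.
- A placebo patient who crosses over stops contributing saline follow-up at that point.

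A return between the end of close follow-up and the three-month contact is a separate problem. If that contact yields only yes or no, the return is known to lie in an interval and has no date. How the analyst fills these gaps then decides the number reported. The background names timing as an open question for these blocks, so a durability figure is likely to be read with interest.

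**Working it through.** The plan states no figure for Aim 1c, so there is none to reproduce. The check asks what an average would report under simple rules when the truth is known.

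**Inputs from Section 10.0.** Three-month contact, taken as T = 13 weeks. Injection 2 at 2 to 3 weeks (1 to 4 accepted); 3 weeks used below. The example log covers two weeks, and unblinding is two weeks after injection 2.

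**Assumptions.** Return times are exponential with true mean m. The documents give no duration, so m is varied over 4, 8, 13 and 26 weeks.

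**Formulas.**
- Share returned by T: 1 − e^(−T/m).
- Rule A, average over dated returns only: m − T·e^(−T/m) / (1 − e^(−T/m)).
- Rule B, non-returners entered at T: m·(1 − e^(−T/m)).
- Rule C, average over returners, with returns in the first 2 weeks dated correctly and later ones dated at the 13-week contact.

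**Example, m = 8.** e^(−13/8) = 0.197, so 80% have returned. Rule A: 8 − 13 × 0.197/0.803 = 4.8 weeks, 40% short. Rule B: 8 × 0.803 = 6.4 weeks. Rule C: 22.1% return by week 2 with mean 0.96, and a further 58.2% return by week 13, so (0.221 × 0.96 + 0.582 × 13)/0.803 = 9.7 weeks, which is too long.

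| True mean (weeks) | Returned by 13 weeks | Rule A | A against truth | Rule B | Rule C |
|---|---|---|---|---|---|
| 4 | 96% | 3.5 | −13% | 3.8 | 8.1 |
| 8 | 80% | 4.8 | −40% | 6.4 | 9.7 |
| 13 | 63% | 5.4 | −58% | 8.2 | 10.3 |
| 26 | 39% | 6.0 | −77% | 10.2 | 10.7 |

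**Duration after injection 1.** With T = 3 weeks, Rule A gives 1.3, 1.4, 1.4 and 1.5 weeks for the same four true means. That figure is set almost wholly by the visit schedule.

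**Short durations.** For a true mean of 2 weeks, Rule A at 13 weeks gives 1.98, only 1% short.

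**Sensitivity to shape.** With Weibull times (shape 2) and a 13-week cut, Rule A gives 4.0, 6.9, 8.0 and 8.5 weeks for true means of 4, 8, 13 and 26. The shortfalls are about 0%, 14%, 39% and 67%: smaller, but in the same direction.

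**The case against.** The strongest reply is that the plan names no estimator, so no particular bias can be laid at its door. That is right as far as direction goes. A reader might infer that the average must come out too short, or that it stays near 5 to 6 weeks whatever the truth. Neither is supported. Rule C overshoots for true means of 4 and 8 weeks. Rule B rises with the truth (3.8 to 10.2 weeks), and with no earlier censoring it is exactly the mean restricted to 13 weeks, a sound quantity if labelled as such.

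Three further inferences should be resisted:

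- **Heavy censoring can be read off the site's own series** (17 of 23 improved, 2 back to baseline). Those patients averaged 3.8 blocks and no follow-up length is given, so the series does not show how many remain improved 13 weeks after a second block.
- **Crossover shortens the treatment arm's durations.** It is optional and confined to placebo patients.
- **A three-month comparison of arms would be spoiled by crossover.** None is planned. Section 12.0 compares placebo data from before unblinding with the later open-label results. Section 10.0 also leaves open whether the last injection means the last randomised or the last open-label one.

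It is also fair to say that duration is already collected, through the log and by recall at follow-up visits. If the three-month clinic visit counts as such a visit, recall would cover it; the telephone option is not said to. In either case a response still in progress has no end to report.

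Finally, Section 1.0 presents Aim 1c as a possible subdivision of a single sufficient aim, and Section 4.0 does not list it as an endpoint. That limits its weight. What survives is that return times will be incomplete by design and nothing in the plan handles them.

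**Conclusion.** The point holds as a cheap improvement. An average is the wrong summary for these data, because its value depends partly on the visit schedule and on unstated rules for missing and undated returns. If only dated returns are averaged, the result is too short as an estimate of mean duration: about 13% for a true mean of 4 weeks and 40% to 77% for 8 to 26 weeks. These sizes rest on assumed exponential times and a 13-week cut. The other dating rule can reverse the direction, and with no true duration in the documents the actual size cannot be stated. The primary LCQ comparison does not depend on any of this.

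**What to change.** In Section 1.0, replace the average in Aim 1c with a time-to-event summary, and add its analysis to Section 12.0:

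1. Define symptom return in advance, and restrict the analysis to patients who improved, since the others have nothing to return from.
2. Start the clock at the last randomised injection; for patients who exit at 0/10, this is injection 1.
3. Ask for the date of return at the existing three-month contact, and make that contact for patients who exit at 0/10 as well.
4. Censor at the last contact or the first open-label injection, whichever comes first.
5. Report a Kaplan-Meier median if it is reached, and a mean restricted to three months. Where the date of return is unknown, use an interval-censored estimate.
6. Report durations after open-label injections separately. State that censoring at crossover may be informative in the placebo arm, because patients whose cough is worsening may be likelier to take it up.

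The cost is one date question, a contact for patients who exit at 0/10, and a little more analysis. A median beyond three months would remain unestimated, which the report should say.
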